3.3 Exclusion Criteria

1. Patients receiving any other investigational agents are ineligible.
2. Patients with a history of allergic reactions attributed to compounds of similar chemical or biologic composition to BAL101553 are ineligible. The BAL101553 Investigator Brochure can be referenced for more information.
3. Patients on **drugs that are strong inhibitors and/or inducers of CYP2C9, CYP2C19 or CYP3A4 (including** enzyme-inducing anti-epileptic drugs [EIAEDs]; see [Appendix IV](#)), are not eligible for treatment under this protocol. Patients taking non-EIAEDs are permitted to take part in the study. Patients previously treated with **any of the prohibited concomitant medications listed above** may be enrolled if they have been off of the **medication** for \geq 10 days prior to the first dose of BAL101553.
4. Patients may not be on coumarin anti-coagulants (warfarin, etc.). Heparin, low-molecular weight heparin (LMWH), or other antithrombotic medications are permitted. See Section [4.6](#).
5. Patients with gastrointestinal disease, or those who have had a procedure that is expected to interfere with the oral absorption or tolerance of BAL101553 (e.g., functionally-relevant gastrointestinal obstruction, or frequent vomiting unresolved upon anti-emetic supportive care), are ineligible.
6. Patients with peripheral neuropathy \geq Common Terminology Criteria for Adverse Events (CTCAE) grade 2 are ineligible.
7. Patients with ataxia \geq CTCAE grade 2 are ineligible.
8. Patients with known acute or chronic hepatitis B or hepatitis C infection are ineligible.

ABTC # 1601

NCI # ABTC-1601

PI: [name]

[figure not shown]
9. Patients with systolic blood pressure (SBP) \geq 140 mmHg or diastolic blood pressure (DBP) \geq 90 mmHg at the Screening visit are ineligible. Patients with an initial clinic blood pressure (BP) \geq 140/90 mmHg may be included if SBP $<$ 140 mmHg and DBP $<$ 90 mmHg is confirmed in two subsequent BP measurements on the same day.
10. Patients with BP combination treatment with more than two antihypertensive medications are ineligible.
11. Significant cardiac disease or abnormality, including any one of the following:
 - Left ventricular ejection fraction $<$ 50% at Screening (assessed by echocardiography, cardiac MRI or MUGA).
 - QTcF $>$ 470 ms on Screening electrocardiogram (ECG), or a clinically-relevant ECG abnormality.
 - Congenital long QT syndrome.

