9.2.1 Adverse Event Characteristics

Definition - An AE is defined as any unfavorable and unintended sign (including an abnormal laboratory finding), symptom or disease temporally associated with the use of a medical treatment (BAL101553 combined with concurrent radiotherapy) or procedure, regardless of whether it is considered to be related to the medical treatment or procedure (attribution of unrelated, unlikely, possible, probable, or definite).

Recording of Adverse Events - ABTC AE Form

- The Investigator will monitor each patient closely for the development of AEs from the time of the first dose of BAL101553 and record all such events on the ABTC AE Case Report Form. Each single sign or symptom must be reported separately.
- **CTCAE term (AE description) and grade:** The descriptions and grading scales found in the revised NCI CTCAE version 4.0 will be utilized for AE reporting until March 31, 2018. CTCAE version 5.0 will be utilized for AE reporting beginning April 1, 2018. All appropriate treatment areas should have access to a copy of the CTCAE version 5.0. A copy of the CTCAE version 5.0 can be downloaded from the CTEP web site (http://ctep.cancer.gov/protocolDevelopment/electronic_applications/ctc.htm). **You must use one of the CTCAE criteria to define your event.**

Adverse events not included in the CTCAE should be reported under "Other" within the appropriate category and graded 1 to 5 according to the general grade definitions - mild, moderate, severe, life-threatening, fatal or disabling - as provided in the CTCAE or the CTCAE Manual. New AEs may be submitted to the CTEP Help Desk at [REDACTED] for annual evaluation by the CTCAE Change Management Committee.

- All AEs should be followed up in accordance with good medical practice. Abnormalities of laboratory events which, in the opinion of the Investigator, constitute AEs (even if not serious) should be followed.
- **Attribution of the AE:** The Investigator will be asked to document his/her opinion of the relationship of the event to study medication as follows:
 - *Unrelated* - The AE is clearly not related to the investigational agent(s).
 - *Unlikely* - The AE is doubtfully related to the investigational agent(s).
 - *Possible* - The AE may be related to the investigational agent(s).

- *Probable* - The AE is most likely related to the investigational agent(s).
- *Definite* - The AE is clearly related to the investigational agent(s).

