5.4.3 Adverse events

Treatment-emergent events are defined as all events occurring after BAL101553 treatment begins. Any adverse event starting prior to the first study drug administration will be reported as medical history. The relationship of an AE to study drug and RT is recorded as unrelated, unlikely, possible, probable, or definite.

For analysis purposes, ‘related to BAL101553’ AEs will be those reported as possible, probable, definite, or those for which the relationship is unknown.

Adverse events will be presented in data listings including dose level, patient, dates/times, study day of event, MedDRA SOC, PT, duration of the event, seriousness, CTCAE grade, intensity, drug adjustment, treatment taken, relationship to study drug, relationship to RT, and outcome.

An overview table (including only treatment-emergent AEs) will also be presented with the number (and percentage) of patients and number of events with:

- Any AE
- Related to BAL101553 AEs
- CTCAE grade 3/4 AEs
- CTCAE grade 3/4 related AEs
- SAEs
- Related SAEs
- AEs leading to dose modifications (i.e., dose reduced or dose interrupted)
- Related AEs leading to dose modifications (i.e., dose reduced or dose interrupted)
- AEs leading to study drug discontinuation
- Related AEs leading to study drug discontinuation
- AEs leading to death
- Related AEs leading to death.

This table will be displayed by dose level.

All treatment-emergent AEs and treatment-emergent AEs related to treatment will be summarized by incidence rate tables broken down by:

- SOC and PT.
- SOC, PT, and worst CTCAE grade.
- SOC, PT, and drug relationship.

Serious treatment-emergent AEs, treatment-emergent AEs leading to dose modifications, leading to study drug discontinuation, or leading to death will be also summarized by SOC and PT. The same analyses will be repeated for related AEs.

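### The treatment-emergent definition goes by onset date alone, so symptomatic worsening of a pre-existing condition is left out of the AE tables unless sites enter it as a new event, which neither document settles

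*SAP*

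**What the plan says.** SAP 5.4.3 gives the definition in two sentences. The first is inclusive: "Treatment-emergent events are defined as all events occurring after BAL101553 treatment begins". The second disposes of anything earlier: "Any adverse event starting prior to the first study drug administration will be reported as medical history". Neither mentions a change in grade.

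The summaries in the same section are then limited to treatment-emergent events:

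- Overview: "An overview table (including only treatment-emergent AEs) will also be presented".
- Incidence tables by SOC and PT, worst grade and relationship: "All treatment-emergent AEs and treatment-emergent AEs related to treatment will be summarized by incidence rate tables broken down by".
- Further tables: "Serious treatment-emergent AEs, treatment-emergent AEs leading to dose modifications, leading to study drug discontinuation, or leading to death will be also summarized".

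Medical history (SAP 5.1.4) is summarised by dose level, SOC and PT only.

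On recording, Protocol 9.2.1 says: "The Investigator will monitor each patient closely for the development of AEs from the time of the first dose of BAL101553". It adds: "Each single sign or symptom must be reported separately". It does not say whether a rise in grade of an existing symptom is a separate report with its own onset date. The schedule of observations (Protocol 9.1, repeated in SAP 2.4.1) includes an AE evaluation at baseline.

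Protocol 3.3 excludes peripheral neuropathy and ataxia only from a set grade upward; the neuropathy criterion ends "CTCAE) grade 2 are ineligible", and the ataxia criterion uses the same grade. Grade 1 of either may therefore be present at entry.

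**The concern.** A definition of treatment-emergence normally has two limbs: new onset after the first dose, or worsening after the first dose of something already present. The SAP has only the first.

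The gap matters more here than in many trials. Patients have glioblastoma, have had a biopsy or resection, and may enter with a Karnofsky status as low as 60%. The toxicities reported for this drug overlap with symptoms such patients may already have: gait disturbance with peripheral neuropathy in the 2-hour infusion study, hallucinations at 30 mg per day by mouth in solid tumours, fatigue and seizures in the GBM arm of the oral study (all Protocol 2.2), and encephalopathy at 8 mg with radiotherapy (Protocol 6.1).

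Safety and tolerability is the first secondary objective. Protocol 11.3 promises type, severity and frequency of toxicity by dose, with no treatment-emergent restriction, and SAP section 6 does not list that restriction as a change. At stake is whether the by-dose AE tables show neurological and constitutional worsening completely.

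**Working it through.** The plan gives no figure to reproduce. The check is to follow one type of event through the two documents and then to bound the number affected.

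**Following an event.** Take a patient with grade 1 ataxia at baseline whose ataxia rises to grade 2 during treatment and settles within two weeks. Under Protocol 5.1, a grade 2 neurological toxicity that resolves within that time does not meet the criterion for neurological toxicity that interferes with daily living and persists. Assume that no other DLT criterion is met.

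1. *The record keeps its pre-dose onset.* The second sentence of the SAP definition makes it medical history. It is then outside the overview, incidence, serious, dose-modification, discontinuation and death tables. Medical history carries neither grade nor relationship, so the increase appears in no summary.
2. *The site opens a new record dated at the worsening.* The onset is after the first dose, the first sentence applies, and the event is counted at its new grade.

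Both routes are compatible with the text. Because a baseline AE evaluation is scheduled, records with a pre-dose onset are foreseeable.

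**What other outputs catch.**

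| Type of worsening | Planned output | Summarised against baseline? |
|---|---|---|
| Laboratory | Shift tables, baseline to worst grade (SAP 5.4.4) | Yes |
| Vital signs | Change from baseline (SAP 5.4.5) | Yes |
| QTcF | Change from baseline and outlier categories (SAP 5.4.6, 5.4.6.1) | Yes |
| DLT | Listing (SAP 5.4.1) | Listed, whatever the flag |
| Neurological examination, MMSE | Listing (SAP 5.4.10) | No |
| Symptoms below DLT (ataxia, neuropathy, fatigue, seizure) | AE tables only | Only by route 2 |

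The exposed cell is the last one.

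**Size.** Let N be the number of patients, p the share with a baseline symptom, q the share of those who worsen, and r the share of worsenings that keep the pre-dose onset. The number missing is N × p × q × r.

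- N = 26 (SAP 2.4.2).
- p = 0.30 to 0.60 and q = 0.10 to 0.20 are assumptions; the documents give neither.
- r = 0 to 1, because the documents do not fix the recording rule.

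Results:

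- r = 0: 0 patients.
- r = 1, low ends: 26 × 0.30 × 0.10 × 1 = 0.78 patients (0.78/26 = 3%).
- r = 1, high ends: 26 × 0.60 × 0.20 × 1 = 3.12 patients (3.12/26 = 12%).

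The range is 0 to about 3 patients. The tables are by dose level, and five patients are planned per level (Protocol 4.2.2), so one missing patient moves a rate at that level by 1/5 = 20 percentage points.

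**The case against.** The strongest reply is that the protocol's own text leans towards counting the worsening. Protocol 9.2.1 defines an AE as an unfavourable sign or symptom associated in time with treatment, and a rise in grade after dosing fits that. Several rules in Protocol 5.1 to 5.3 accept return to the baseline level as recovery, which presumes that deterioration above an existing baseline is handled as an on-study event. The medical-history sentence may be meant only to place findings from the baseline AE evaluation. Whether a grade change opens a new record is a data-entry convention, and the AE form and its completion instructions are not among the documents.

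This stands as far as it goes: the loss is possible, not certain. It does not close the gap. The recovery rules govern dosing and removal from treatment; they do not set an onset date. The SAP sentence that assigns pre-dose events to medical history has no exception, and a programmer applying it as written would classify by start date. If sites differ in how they enter worsening, the tables mix two conventions and the reader cannot tell.

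It is also right that the primary endpoint is safe. DLTs are defined in Protocol 5.1 by grade, attribution and duration, with no condition on treatment-emergence, and the MTD-determining population (SAP 3.4) does not use the flag. Expedited SAE reporting (Protocol 9.3.2) is equally independent of it.

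**Conclusion.** The definition is incomplete and should be corrected. Symptomatic worsening of a pre-existing condition, short of a DLT, drops out of the treatment-emergent tables by dose unless it was entered as a new event, and neither document specifies that. Under the assumed ranges this concerns 0 to about 3 of 26 patients. The true number depends on the prevalence of baseline symptoms, on how often they worsen, and on site practice, none of which the documents give.

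Two stronger readings are not supported:

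- A reader might infer that such worsening is lost from every AE table. That holds only for records that keep their pre-dose onset.
- A reader might infer that rates of grade 3 or higher toxicity are understated. That could happen, but nothing in the documents allows an estimate of how many worsenings would reach grade 3, and the range above counts worsening of any size.

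Nor should the population be described as entering straight from surgery: Protocol 3.2 requires recovery from the immediate post-operative period. The point rests on grade 1 ataxia and neuropathy being allowed, and on other symptoms such as fatigue or seizure that may precede dosing.

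**What to change.** Replace the two sentences in SAP 5.4.3 with a definition that has both limbs. A treatment-emergent AE is one that starts on or after the first dose of BAL101553, or that was present before the first dose and increases in CTCAE grade on or after it. It is graded at its worst post-dose grade. Keep as medical history only pre-dose conditions that do not worsen.

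Also state how worsening reaches the dataset: either it is entered as a new AE record dated at the increase, or it is derived by comparing the worst post-dose grade with the baseline grade. If both can occur, say that a patient is counted once per preferred term.

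The cost is small: a revised definition, one derivation, and targeted queries before database lock for pre-existing conditions whose baseline grade was not recorded. The queries are the main burden, because medical history is summarised without grade and the documents do not show that baseline grade was collected for every symptom. The SAP was written while the study was ongoing, so the change can be made in the plan instead of being explained afterwards in the study report.

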5.4.4 Laboratory evaluation

The laboratory tests for safety analyses comprise the following:

- Hematology: Hemoglobin, Platelet count, White blood cell count, Neutrophil count, Lymphocyte count,
- Serum biochemistry: Sodium, Potassium, Creatinine, Albumin, Alkaline phosphatase, Total and direct bilirubin, Aspartate amino transferase, Alanine amino transferase, Phosphate (inorganic phosphorus), Calcium, Magnesium.
- Cardiac troponin: Cardiac Troponin I, Cardiac Troponin T
- Coagulation: International normalized ratio, Partial Prothrombin Time and activated Partial Thromboplastin Time.

Laboratory values will be converted into SI units and the severity grade determined based on CTCAE.

Descriptive statistics for each laboratory analyte at each assessment time will be tabulated by dose level. The change from baseline will also be summarized by dose level.

An analysis of individual patient changes by dose level will be presented using shift tables showing the change from CTCAE grade/intensity at baseline to the worst CTCAE grade/intensity (including unscheduled assessments) during the study.

The laboratory parameters will be presented in data listings sorted by dose level, patient, study day, study time, and analyte. Out-of-range values will be flagged with h (high) or l (low).

5.4.5 Vital signs

Summary statistics by dose level and scheduled time point will be presented for each vital sign. The change from baseline will also be presented.

The mean maximum change from baseline (the average of the maximum change between baseline and all timepoints post baseline) will also be presented.

The number of patients with values outside marked reference ranges will also be tabulated by dose level and scheduled time point.

The vital signs marked reference ranges are:

- Diastolic blood pressure: < 60 mmHg or > 100 mmHg.
- Systolic blood pressure: < 80 mmHg or > 180 mmHg.
- Pulse: < 40 beats/min or > 120 beats/min.
- Temperature: < 36.0 degrees Celsius or > 38.5 degrees Celsius.

Vital sign assessments will be presented for each patient in a data listing by dose level.

5.4.6 ECG results

The 12-lead ECG results (QTcF interval reported in the CRF) and changes from baseline will be summarized using standard descriptive statistics by dose level and scheduled time point.

ECG results will be presented for each patient in a data listing by dose level.

5.4.6.1 Outlier analysis

The number and percentage of patients with maximum on-treatment value of QTcF interval, categorized as ≤ 450 msec, > 450 msec and ≤ 480 msec, > 480 msec and ≤ 500 msec, and > 500 msec, as well as maximum on-treatment change from baseline value of QT/QTc intervals, categorized as < 5 msec, ≥ 5 msec and < 10 msec, ≥ 10 msec and < 20 msec, ≥ 20 msec and < 30 msec, ≥ 30 msec and < 60 msec, and ≥ 60 msec will be tabulated based on scheduled and unscheduled 12-lead ECG measurements.

5.4.7 Physical examination

General physical examination assessments will be listed by dose level, patient, and study day.

5.4.8 Prior and concomitant medications

Medications and significant non-drug therapies prior to and after first administration of the study drug will be listed by dose level and patient.

5.4.9 MRI Scan

MRI Scan results will be presented for each patient in a data listing by dose level.

5.4.10 Neurological examination

Neurological and Mini-Mental State examination results will be presented for each patient in a data listing by dose level.

6 CHANGES FROM THE PLANNED ANALYSIS IN STUDY PROTOCOL

OS and PFS will use the “Day1 dosing” date instead of “initial diagnosis” date as starting point. For OS, event rate will not be estimated, only median and quartiles will be estimated using Kaplan-Meier method.

Only the number and percentage of patients who experienced grade 3 or above toxicity will be displayed, no 95% CI confidence interval will be estimated.
